The primary endpoint is to evaluate the **safety and tolerability** of concurrent single/low dose radiotherapy (8 Gy/1fx) in combination with pembrolizumab in relapsed and/or refractory myeloma patients at 3 months (**acute toxicity, primary endpoint**) and at 6 and 12 months (**late toxicity**). The secondary objective is to characterize the effect of radiation in combination with pembrolizumab on systemic response rates using international myeloma working group (IMWG) uniform response criteria for myeloma, to assess baseline changes in PET/CT as a result of combining pembrolizumab and radiotherapy, and to evaluate treatment response at irradiated and un-irradiated sites (i.e. the abscopal effect) using baseline PET/CT. Exploratory analysis would include analyzing Circulating Myeloma Tumor cells and phenotype of T cells as a prognostic and predictive biomarker. Compare blood Myeloma tumor cells with BM tumor cells. We are interested in comparing T cell phenotype after each treatment and using that as a prognostic biomarker. We will also evaluate serum LDH, CRP, ESR, ALC, cytokines and chemokines (such as IL-6, s IL-6R) and other immune related biomarkers, and correlate their expression pre and post treatment and evaluate changes in bone marrow biopsy and peripheral blood for mutational load, mutational signature (whole exome sequencing), transcriptome of the T cells, mutation specific T cells, PD1 and PDL1 expression on MM cells and T cells by flow/IHC, RNA-seq. Other biomarker correlative exploratory analysis (role of exosomes, etc) may also be pursued as ancillary research to this trial;

2. Acute Toxicity and Late Toxicity Assessment:

[figure not shown]
Acute toxicity (i.e. > Grade 2 CTCAE toxicity at **3 months**) associated with radiation therapy at the **radiated site** will be analyzed as the **primary safety endpoint** in this pilot study; Goal would be to see less than 20% > grade 2 toxicity at 3 months within the radiated area.

CTCAE criteria (see Appendix I) will be applied to assess acute toxicity.

Other endpoints that may be analyzed include late toxicity (> Grade 2 CTCAE toxicity at the radiated site at **6 months and 12 months**), systemic response against myeloma burden to localized radiation and pembrolizumab using IMWG uniform criteria, as well as other endpoints (defined in more detail in section 3.0).

3. Trial Schema

Figure 1: Trial Overview

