3. OBJECTIVES, ENDPOINTS & HYPOTHESES

1. Primary Objective, Endpoint, & Hypothesis

Primary Objective

To evaluate the safety of concurrent single/low dose radiotherapy (**8 Gy/1fx**) in combination with Pembrolizumab in relapsed or refractory myeloma patients; **Once 10 patients are enrolled, we will stop trial for 3 months to assess for acute toxicity, and then resume the trial.**

Primary Endpoint

CTCAE > grade 2 toxicity at the specific irradiated **organ site at 3 months** (the Dose Limiting Toxicity);

Primary Hypothesis

The primary hypothesis of this pilot study is that the use of concomitant Pembrolizumab and radiation therapy in multiple myeloma patients will be well tolerated and safe.

Alternative Hypothesis

It is possible that concurrent use of radiotherapy and Pembrolizumab in relapsed/refractory myeloma may increase CTCAE > grade 2 toxicity within the radiated site at 3 months.

2. Secondary Objective(s), Endpoint(s) & Hypothesis (es)

Secondary Objectives

To characterize late toxicity (CTCAE > grade 2 toxicity at **6 and 12 months**) and the effect of radiation in combination with Pembrolizumab on systemic response rates using international myeloma working group (IMWG) uniform response criteria for multiple myeloma at **6 months and 12 months**;

To assess changes in PET/CT as a result of combining Pembrolizumab and radiotherapy at **6 months and 12 months**;

Secondary Endpoints

- a. 1. Number of patients achieving any response (from baseline) per IMWG response criteria at **6 months and 12 months**;
- b. 2. Overall survival time at **6 months and 12 months**;
- c. 3. Overall response based on baseline changes on PET/CT at **6 months and 12 months**;
- d. 4. Difference in pre and post treatment serum immune biomarkers;

Secondary Endpoint Definitions

- a. Response is defined per IMWG criteria, and will be calculated at **6 months and 12 months**;
- b. Overall survival will be defined as time from first treatment on cycle 1, day 1 to the earlier of date of death and/or last follow up at **6 months and 12 months**.
- c. Overall response will be defined using IMWG uniform response criteria.
- d. Several serum biomarkers will be analyzed.

Secondary Hypotheses

The secondary hypothesis is that low dose/single fraction (8Gy/1fx) will synergize with Pembrolizumab for a more effective anti-myeloma response per IMWG, via the radiation induced abscopal response.

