4.4 Safety and toxicity of Pembrolizumab

Pembrolizumab has been administered to a total of 308 melanoma patients, from 2 prospective clinical trials¹¹. The first trial administered pembrolizumab at 3 different doses (2mg/kg q3weeks, 10mg/kg q3weeks, and 10mg/kg q2weeks) for 4 total cycles, followed by continued maintenance therapy until progression. Overall, 79% of patients develop any grade of toxicity. The most common toxicities were fatigue (30%), rash (21%), pruritus (21%), and diarrhea (20%). However, most of these symptoms were low grade, as only 13% developed grade 3- 4 toxicities. Furthermore, grade 3-4 adverse events were dose related: the 10mg/kg,

q2week cohort was 23%, while the q3week cohorts was 4-9%. The grade 3 clinical toxicities documented included rash (2%), pruritus (1%), hypothyroidism (1%), diarrhea (1%), abdominal pain (1%), decreased appetite (1%), elevated AST (1%), and renal failure (1%). In the 2 cases of renal failure, both cases improved with discontinuation of pembrolizumab and initiation of glucocorticoid therapy

In the trial of pembrolizumab in advanced melanoma patients, the toxicity profile was similar to that reported by Hamid et al: 82% developed any grade of toxicity, while 12% developed grade 3-4 toxicities. Most common toxicities were fatigue, pruritus, and rash. Reported grade 3-4 toxicities included fatigue (3%), elevated amylase (<1%), anemia (<1%), autoimmune hepatitis (<1%), confusion (<1%), diarrhea (<1%), dyspnea (<1%), encephalopathy (<1%), hypophysitis (<1%), hypoxia (<1%), muscular weakness (<1%), musculoskeletal pain (<1%), pancreatitis (<1%), peripheral motor neuropathy (<1%), pneumonitis (<1%), rash (<1%), rash maculopapular (<1%). Overall 6 patients (7%) developed adverse events leading to discontinuation of the drug. 3 of these cases (3%) were immune mediated. No drug related grade 5 toxicities were reported. Other side effects that have been discovered include vasculitis and hypothyroiditis (refer to latest investigator brochure accompanying the trial).

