selection ranging from 4 MeV – 20 MeV. For deeper seated tumors, photon therapy should be used with energy range of 4MV – 18 MV, based on appropriate coverage of the PTV. The goals should be to provide adequate coverage, while minimizing hot spots as well as scattered radiation dose to the surrounding structures.

A range of radiation fields are allowed. A single beam, an AP/PA, or multiple beams are allowed. A range of radiation techniques (2D, 3DCRT, IMRT, IMRS) are allowed;

Institutional standard of care protocol will be followed when assessing adequate PTV coverage and dose volume histogram normal tissue limits.

Radiation Toxicity Evaluation

Patients should undergo evaluation for development of acute and chronic radiotherapy toxicity at the time of protocol visits. This should be done at **1 month +/- 2 weeks** after completing radiotherapy and **every 3 months for at least 1 year**. Toxicity will be graded per CTCAE 4.0 adverse events grading system. If there is a suspicion of a novel or unexpected toxicity of grade 3 or higher severity that is suspected to be related to the combination of pembrolizumab and radiotherapy, the study coordinator should be immediately notified. If possible, a determination should be made whether the toxicity is likely to be the result of immune therapy, radiotherapy, or was exacerbated by the combination. The AE or SAE should be attributed as definite, probable, possible, or unlikely for each.

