11. STATISTICAL ANALYSIS PLAN

1. Statistical Analysis Plan Summary

Study Design

The study is a pilot study to look at the safety of concurrent PD-1 inhibitor and SRS for relapsed/refractory myeloma. A total of 24 patients will be enrolled on the trial (20 is the minimum, with an additional 4 patients, to make for any attrition and/or loss to follow-up). 12 patients will be allowed to not have measurable myeloma disease in this trial. Once 10 patients are enrolled, we will stop trial for 3 months to assess for acute toxicity, and then resume the trial. The estimated exact Clopper-Pearson 95% confidence interval for a 20% rate based on 5 responses in 20 patients is (0.087, 0.491), with a precision of 0.185. If we see lower than 20% difference in rate of toxicity at 3 months, the combination will be deemed safe.

A minimum of 20 patients are required to complete full treatments. An additional 20% is allowed for drop out/failure to adhere to required follow-up and treatment recommendations. Thus, 24 patients will be allowed to be enrolled on the trial to make for any attrition and/or loss to follow-up. 12 patients will be allowed to not have measurable myeloma disease.

# of Responses / # of Patients	95% confidence interval
5 / 20	(0.087, 0.491)
6 / 24	(0.098, 0.467)

Populations for analysis

- Enrolled set: All subjects who signed an informed consent.
- Safety set: All subjects who received at least one dose of any study drug.
- Full analysis set: All subjects from the safety set who have the required follow-up and treatment adherence to evaluate response and safety over time.

2. Statistical Analyses

1. Response

IMWG criteria will be used to assess response. Proportion of patients achieving stable

disease or better will be reported at **6 months** and **12 months**; Response rates will be reported along with 95% confidence intervals will be estimated using the Clopper-Pearson method.

2. Safety

Proportion of acute (at **3 months**) and late toxicity (**6 and 12 months**) will be reported, and 95% confidence intervals will be estimated using the Clopper-Pearson method.

3. Overall Survival

For overall survival, death from any cause will be defined as the event. Patients will be censored at time of last follow-up. OS will be estimated using the Kaplan-Meier product-limit method. Overall survival will be analyzed at **6 months, and 12 months**.

4. Biological variables

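### The SAP's safety conclusion is about the combination, but the endpoint behind it covers only toxicity at the irradiated site

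*Combined protocol and SAP*

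**What the plan says.** The decision rule is in Section 11, Statistical Analysis Plan Summary, Study Design: "If we see lower than 20% difference in rate of toxicity at 3 months, the combination will be deemed safe". It does not say where in the body the toxicity must occur.

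Other sections supply the location:

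- Section 3, Primary Endpoint: "CTCAE > grade 2 toxicity at the specific irradiated organ site at 3 months (the Dose Limiting Toxicity".
- Section 3, Alternative Hypothesis: the combination "may increase CTCAE > grade 2 toxicity within the radiated site at 3 months".
- Section 2, Acute Toxicity and Late Toxicity Assessment: "Goal would be to see less than 20% > grade 2 toxicity at 3 months within the radiated area".
- Section 9.1, Table 4 footnote: CTCAE toxicity is graded at the radiated site at 3, 6 and 12 months.

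The primary hypothesis in Section 3 is wider. It states that "the use of concomitant Pembrolizumab and radiation therapy in multiple myeloma patients will be well tolerated and safe". The introduction to Section 4 says the results are meant to inform later trial designs and clinical management.

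Section 11, Statistical Analyses, item 2 (Safety) plans proportions of acute and late toxicity with Clopper-Pearson intervals. It has no separate item for immune-related or other systemic events.

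**The concern.** A local endpoint is being used to support a conclusion about the whole regimen. Choosing a site-specific endpoint is legitimate, because excess toxicity in the field is a natural question when radiation is added to a checkpoint inhibitor. But a low rate in the field says nothing about pneumonitis, colitis or hepatitis arising elsewhere. Section 6 itself expects such events, warning that immune-related events can involve several body systems and giving management tables for them.

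What is at stake is the trial's headline statement. Readers planning later studies could take it as evidence on overall tolerability that the rule never examined.

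**Working it through.** **1. The plan's own intervals.** The Clopper-Pearson limits for x events in n patients are the 0.025 quantile of Beta(x, n−x+1) and the 0.975 quantile of Beta(x+1, n−x).

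- 5/20 gives (0.0866, 0.4910); the SAP states (0.087, 0.491).
- 6/24 gives (0.0977, 0.4671); the SAP states (0.098, 0.467).

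Both reproduce.

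**2. What enters the rule.** I read the rule as an observed rate below 20%, following the goal in Section 2, since a single-arm trial has no comparator for a difference.

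| n | Largest passing count of site events | Next count |
|---|---|---|
| 20 (minimum) | 3 (3/20 = 15.0%) | 4/20 = 20.0%, fails |
| 24 (planned) | 4 (4/24 = 16.7%) | 5/24 = 20.8%, fails |

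The only argument is the number of patients with site toxicity above grade 2. The number with severe toxicity outside the irradiated organ does not appear.

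**3. A constructed example.** Suppose 0/24 patients have a site event and 6/24 have a grade 3 or higher event elsewhere.

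- Site: observed 0%; upper 95% limit 1 − 0.025^(1/24) = 0.1425, or 14.2%. The rule is met.
- Elsewhere: 6/24 = 25%, 95% CI 9.8% to 46.7%. The rule is unaffected.

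**4. How insensitive the rule is.** The documents give no expected site rate, so I assume 5%, with a range of 0% to 10%.

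- n = 20: P(rule met) = P(Bin(20, 0.05) ≤ 3) = 0.984; 1.000 at a site rate of 0% and 0.867 at 10%.
- n = 24: P(rule met) = P(Bin(24, 0.05) ≤ 4) = 0.994; 0.915 at a site rate of 10%.

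For a fixed site rate these values are the same whatever the rate of severe toxicity elsewhere.

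For scale, suppose severe toxicity at any site were held to the same 20% cut, with site and systemic events independent. With systemic rate s, the any-site rate is p = 1 − 0.95(1 − s). For n = 20:

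| s | p | P(below 20%), any site | P(rule met), site only |
|---|---|---|---|
| 13% | 0.174 | 0.534 | 0.984 |
| 30% | 0.335 | 0.059 | 0.984 |
| 40% | 0.430 | 0.008 | 0.984 |

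This shows how far the two questions differ. It is not a proposed criterion.

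**The case against.** **The SAP sentence is not limited to the irradiated site.** This is correct as far as its wording goes, and the Safety item in Section 11 names no site either. The restriction is imported from Sections 2, 3 and 9.1. It is still the better reading, because those sections define the primary endpoint and attach the 20% figure to the radiated area. If the SAP meant any toxicity, it would contradict them on the primary numerator and would still need a definition.

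**Other safeguards exist.** This also stands. Section 7 allows early termination for the incidence or severity of adverse reactions. Section 10 requires expedited reporting of serious events and events of clinical interest. The Section 13.0 committee reviews aggregate toxicity. Deaths from any cause enter the survival analysis. A reader might infer that the plan would call the combination safe whatever the rate of severe systemic toxicity. That is true of the rule, not of the plan as a whole: a trial with extreme systemic toxicity might be stopped before the rule was applied. None of these safeguards carries a rate or alters the rule.

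**No immune-related event could count.** A reader might infer this too, but it goes too far. An immune-related event in the irradiated organ would count; only events outside it are excluded.

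**Sizing from cited drug rates.** It is tempting to use Section 4.4, where for grade 3-4 events the "q2week cohort was 23%, while the q3week cohorts was 4-9" percent, and 13% overall. Over 24 patients, 4% to 13% gives 24 × 0.04 = 0.96 to 24 × 0.13 = 3.12 events. These are melanoma figures with no stated 3-month window, so they do not size this problem. Events at a drug-alone background rate would not show that the combination is harmful either.

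**Attribution.** Section 8 says that, where possible, "a determination should be made whether the toxicity is likely to be the result of immune therapy, radiotherapy, or was exacerbated by the combination". This follows a sentence about suspected novel or unexpected toxicity of grade 3 or higher. The general causality assessment in Section 10, Table 6 covers the pembrolizumab product only. Routine attribution of every event to radiation or to the combination cannot be assumed, so a remedy should not depend on it.

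**Conclusion.** The point holds as a mismatch of scope. The rule's conclusion is about the combination, while its numerator, as defined elsewhere in the protocol, is toxicity above grade 2 at the irradiated site at 3 months. Severe toxicity outside the irradiated organ is neither an input to the rule nor the subject of a planned analysis.

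The structural point needs no assumed rate. The 0/24 and 6/24 example is illustrative and carries no probability. The probabilities rest on an assumed 5% site rate (0% to 10%) and, for the any-site comparison only, on independence. All rest on reading the rule as an observed rate below 20%.

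This should be corrected before results are reported. The site-specific endpoint looks deliberate and can stay. Oversight of participants does not depend on the sentence at issue; the validity of the headline conclusion does.

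**What to change.** 1. In Section 11, Study Design, define the numerator as CTCAE toxicity above grade 2 at the irradiated site at 3 months, and limit the conclusion to acceptable acute toxicity at that site.
2. In Section 11, Statistical Analyses, item 2, add the proportion of the safety set with any grade 3 or higher adverse event at any site through 3 months, regardless of attribution, with a Clopper-Pearson 95% CI. Optionally add the pembrolizumab-related subset, using the causality recorded under Section 10, Table 6.
3. Present both results alongside any statement about the safety of the combination. The added table is descriptive; no threshold is proposed for it.

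One detail to settle: Sections 7 and 10 end collection of non-serious adverse events 30 days after treatment stops. The SAP should therefore say how patients who stop well before 3 months are shown in the new table.

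The cost is SAP wording and one table from adverse event data already collected, with no new patients or procedures. The claim becomes narrower.

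### The 3-month toxicity rate behind the only numerical safety rule has no stated scoring window and no assigned analysis set, and either choice can reverse the verdict

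*Combined protocol and SAP*

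**What the plan says.** **Endpoint and rule.** Section 3 defines the primary endpoint as "CTCAE > grade 2 toxicity at the specific irradiated" organ site, timed at 3 months. Section 2 sets the target: "Goal would be to see less than 20% > grade 2 toxicity at 3 months within the radiated area". Section 11 turns it into a verdict: "If we see lower than 20% difference in rate of toxicity at 3 months, the combination will be deemed safe". A footnote to the flow chart in Section 9.1 asks for one radiated-site score at each of months 3, 6 and 12.

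**Text pointing to a period instead.** Section 2 calls the endpoint acute toxicity and Section 3 calls it "the Dose Limiting Toxicity". Section 3 also says: "Once 10 patients are enrolled, we will stop trial for 3 months to assess for acute toxicity, and then resume the trial". Section 8 has radiation toxicity evaluated from 1 month onward. In the flow chart, the CTCAE toxicity row is marked, as the table was extracted, under the 3-weekly and 6-weekly columns and not under the 3-monthly one. Section 10 has adverse events graded throughout, with each change of grade recorded.

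**Analysis sets.** Section 11 defines "Safety set: All subjects who received at least one dose of any study drug" and "Full analysis set: All subjects from the safety set who have the required follow-up and treatment adherence to evaluate response and safety over time". Its Safety paragraph promises proportions with Clopper-Pearson intervals but names neither set. On numbers it says: "An additional 20% is allowed for drop out/failure to adhere to required follow-up and treatment recommendations", which gives 24 enrolled for a minimum of 20. No rule covers a patient who has had no event and has no 3-month assessment.

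**The concern.** Both parts of the primary proportion are open. For the numerator, a literal reading of the time point leaves out an event above grade 2 that follows the day-1 fraction and settles before the visit. It would be on file as an adverse event, but nothing brings it into the primary rate. For the denominator, the set whose description mentions safety over time removes patients who lack follow-up or adherence. The Safety set turns on a dose of study drug, although the endpoint concerns the irradiated site; a patient irradiated on day 1 but never given pembrolizumab might be left out, probably a rare case.

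At these sample sizes one or two events decide whether the target is met. The trial is open-label, so a window and a set left unspecified could be settled after the data are known.

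**Working it through.** **The plan's own figures.** Exact Clopper-Pearson limits give 0.0866 to 0.4910 for 5/20 and 0.0977 to 0.4671 for 6/24. Both intervals in Section 11 reproduce.

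**Where the cut falls.** I read the rule as an observed rate below 20%, in line with the Section 2 target; the word *difference* in Section 11 has no comparator in a single-arm study.
- n = 20: 3/20 = 15.0% meets it, 4/20 = 20.0% does not. Goal met if X ≤ 3.
- n = 24: 4/24 = 16.7% meets it, 5/24 = 20.8% does not. Goal met if X ≤ 4. The same cut of 4 applies for n = 21 to 23.

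**Effect of the window.** Let p be the cumulative rate by month 3 and f the share of events settled before the visit. A single look sees q = p(1 − f), and the chance of meeting the goal is P(X ≤ 3 | 20, q). Both p and f are assumptions, because the documents give no irradiated-site rate. The 12–13% grade 3–4 figures in Section 4.4 are whole-body pembrolizumab toxicity in melanoma.

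| p | f = 0 | f = 0.25 | f = 0.50 | f = 0.75 |
|---|---|---|---|---|
| 5% | 0.984 | 0.994 | 0.999 | 1.000 |
| 10% | 0.867 | 0.942 | 0.984 | 0.999 |
| 15% | 0.648 | 0.819 | 0.942 | 0.994 |
| 20% | 0.411 | 0.648 | 0.867 | 0.984 |
| 30% | 0.107 | 0.310 | 0.648 | 0.942 |
| 40% | 0.016 | 0.107 | 0.411 | 0.867 |

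Example: p = 30% and f = 0.50 give q = 15%, and P(X ≤ 3 | 20, 0.15) = 0.648, against 0.107 when every event counts.

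**Effect of the set.** Let m of 24 patients fall outside the adherent set. Events are A ~ Bin(24 − m, pk) among those kept and K ~ Bin(m, r) among those outside. The sets disagree when only one of A/(24 − m) and (A + K)/24 is below 20%. The probability of disagreement is:

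| m | pk | r = 0 | r = 20% | r = 40% |
|---|---|---|---|---|
| 1 | 10% | 0 | 0.024 | 0.048 |
| 1 | 20% | 0 | 0.041 | 0.082 |
| 2 | 10% | 0 | 0.048 | 0.104 |
| 2 | 20% | 0 | 0.083 | 0.163 |
| 3 | 10% | 0 | 0.072 | 0.167 |
| 3 | 20% | 0 | 0.126 | 0.244 |
| 4 | 10% | 0.090 | 0.079 | 0.169 |
| 4 | 20% | 0.218 | 0.130 | 0.162 |

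Direction:
- With m = 1 to 3, every disagreement is the adherent set alone meeting the goal, for example 4/22 = 18.2% against 5/24 = 20.8%.
- With m = 4 it runs both ways: 3/20 = 15.0% against 5/24 = 20.8%, or 4/20 = 20.0% against 4/24 = 16.7%. At pk = 20% and r = 20%, the 0.130 splits into 0.041 (adherent set alone meets it) and 0.089 (all 24 alone meet it).
- Disagreement is not greatest at the planned allowance of 4: at pk = 20% and r = 40%, three outside give 0.244 and four give 0.162.

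**Unassessed patients.** With 4 event-free patients unassessed and one event seen, the bounds on 24 are 1/24 = 4.2% and 5/24 = 20.8%. With one unassessed, the bounds straddle 20% only at 4 observed events (16.7% to 20.8%).

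**The case against.** The best reply is that the plan, read as a whole, already means a period. The acute and dose-limiting labels, the 3-month pause, evaluation from 1 month, and the flow-chart row under the 3- and 6-weekly columns all lean that way. That is a fair reading and may be the intended one. But the endpoint, the target, the rule and the flow-chart footnote all use a time point, and no sentence reconciles them. The column position also depends on how the table was extracted. A reader might infer that early events will be lost; the documents show only that a literal application can lose them from the rate, not from the records.

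On the set, a Safety set exists and is by name the obvious one for safety, while the wording about safety over time fits the 6- and 12-month reports at least as well. A reader might also infer that patients stopped for toxicity are dropped, since Section 7 requires discontinuation for unacceptable adverse experiences. No text says that a stop the protocol requires counts as non-adherence, and Section 10 asks for final-visit activities at discontinuation and follow-up of events then present. What stands is that the Safety paragraph assigns no set.

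It is tempting to say that a single look can only lower the rate. That holds for a fixed denominator. If event-free unassessed patients are also dropped, the rate can rise, from 4/24 = 16.7% to 4/20 = 20.0%.

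Finally, this is a pilot with wide intervals, and the early-termination criteria in Section 7 and the monitoring committee in Section 13 also protect patients. True, but neither defines what the trial will report as safe.

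**Conclusion.** The point holds as an inconsistency in the primary rate that should be fixed. It is not evidence that the endpoint will miss toxicity or that the trial lacks safety oversight. The window matters little at a 5% cumulative rate (0.984 against at most 1.000) and a great deal at 20% or more, where the rule has work to do: with half the events settled, 0.411 becomes 0.867 at 20% and 0.107 becomes 0.648 at 30%. The set matters less often but can reverse the result, in either direction when 4 patients are excluded.

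Event rates, settled shares, numbers outside the adherent set and rates among them are all assumptions shown as ranges. The cut points of 3/20 and 4/24, and the absence of an assigned set or missing-data rule, come directly from the documents.

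**What to change.** - **Endpoint.** Define it as the worst CTCAE grade at the irradiated site from radiotherapy through the 3-month visit, and show the grade at that visit alongside. Align Sections 2, 3 and 11 and the flow-chart row and footnote with this definition.
- **Set.** Use all treated patients for the primary rate: the Safety set, stated to include anyone given the study radiotherapy. Present the adherent set as supportive only.
- **Leavers.** Count an event before leaving as an event. For event-free patients without a 3-month assessment, best-case and worst-case bounds are an optional sensitivity analysis. They can be wide, so they should not decide the verdict.

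The cost is wording only: Sections 8 and 10 already collect the data, and no visits or patients are added. The reported rate may be higher.
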